#### Blinding

Allocation concealment is performed by masking the investigators, additional study team performing the ocular measurements, parents and patients to randomization status throughout the entire study period. All statistical analyses will be performed masked to randomization status. A list linking participant study identification number to randomization status will be kept under lock in a designated space unavailable to study investigators. Trial medication will be prepackaged from external collaborator #1 so that bottles are pre-labeled according to the European rules on labelling of trial medicines (see *Appendix 1*) and of similar appearance.

If necessary, sponsor-investigator will be unblinded as to participants treatment status as described above. All statistical analyses will be performed in a masked fashion allowing sponsor-investigator to part of the analyses.

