The effect of atropine is dose dependent with high dose (1%) superior (≥0.50 diopter reduction in myopia/year) to other treatments. (33) However, the side effects of high dose treatment including photophobia related to pupil dilation, reading problems and headache together with the profound myopic rebound effect after treatment cessation make treatment unacceptable for standard care. (40) The Atropine for Treatment of Childhood Myopia (ATOM 2) study (41) compared the safety and efficacy of 3 lower doses of atropine (0.5%, 0.1% and 0.01%). The study was a 60-month doubled masked, randomized, controlled trial including 400 Asian children aged 6-12 years. A washout period of 12 months was included, and surprisingly atropine 0.01% was found superior in reducing myopia progression (-1.4 diopters less) compared to 0.5% and 0.1% after 60-months mainly because of less rebound effect in myopia progression when treatment was stopped. The side effects of atropine 0.01% and 0.1% were low. Pupil size under both photopic and mesopic conditions were only 1 and 3 millimeters, respectively, and accommodation amplitude decreased to 11.3 diopters and 3.8 diopters, respectively. Allergic conjunctivitis was seen in 4.5% of the children in the 0.1% group but in no children in the 0.01% group. (41)

Atropine appears to have the strongest clinical effect on reducing myopia progression of all reported modalities so far, and low-dose treatment seems favorable due to limited side effects and greater longterm effects because of the rebound catch-up myopia seen after treatment cessation with higher doses. However, these results are based on Asian studies, and it is unknown whether similar results can be replicated in Danish children, since environmental factors, heritability and genetics may influence the effect of the treatment.

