## Methods

#### Study design

The study is designed as a randomized, double-masked, multicenter, 36-month prospective, phase II 1:1:1 study of safety and efficacy of 0.1% atropine loading dose to single 0.01% atropine versus placebo. In phase 1 (treatment phase), the participants will be randomized in a 1:1:1 ratio to receive 0.1% atropine loading dose for 6 months followed by 0.01 % atropine for 18 months (n=50) versus 0.01% atropine (n=50) or placebo (n=50) for 24 months. The atropine is administered as one eye drop daily in each eye at bedtime. In phase 2 (washout phase), treatment will be stopped and the participants monitored for 12 months. A schematic presentation of the 3 interventional groups are shown in Figure 1.

Figure 1: A schematic presentation of the 3 interventional groups.

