#### Standard examinations at baseline and month 3, 6, 12, 18, 24, 30 and 36 (approx. 2 hours):

- Best corrected (using "push plus" refraction principle) visual acuity using the HOTV chart that is based on the same principle as the ETDRS chart.
- Cycloplegic auto-refraction performed 30 minutes after the last of two drops of Minims® (Bausch & Lomb, Chauvin Pharmaceuticals Ltd., UK) cyclopentolate 1% separated 5 minutes apart. A minimum of 5 readings are made. In situations of unstable fixation, readings are eliminated if cylinder values deviate more than 1 diopter from values obtained during stable fixation and/or obvious incorrect readings. In situations of more than 5 valid readings, the number is reduced by eliminating readings from the beginning alternating with the end of the set of measurements until 5 readings remain.
- Intraocular pressure (Icare® TAO1i, tonometer, Icare Finland Oy, Vantaa, Finland) with a minimum of 5 readings.
- Axial length measurements (IOLMaster® 700, Carl Zeiss AG, Oberkochen, Germany). Separate measurements are recorded until 5 readings variating less ≤ 0.05 mm are obtained.
- Anterior Eye Segment Tomography by Scheimpflug imaging (Pentacam®, OCULUS Optikgeräte GmbH, Wetzlar, Germany).
- Pupil diameter measurements under different light intensities.
- Swept Source Optical Coherence Tomography chorio-retinal images (DRI OCT Triton, Topcon, Hasunuma-cho, Itabashi-ku, Tokyo, Japan) at baseline and month 6,12,18,24,30 and 36.
- Near visual acuity assessed using best-corrected distance spectacle correction with a reduced logarithm of the minimum angle of resolution (logMAR) reading chart placed at 40 cm under welllit conditions.

 Near point of accommodation measured using a Royal Air Force near point rule using bestcorrected distance spectacle correction. Accommodation amplitude is calculated as the inverse of near point of accommodation.

Figure 2: Time schedule of the study.

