## Risks, side effects and inconveniences

The use of atropine 1% eye drops has been approved for cycloplegia, mydriasis and penalization of the healthy eye in the treatment of amblyopia. The most frequently reported side effects of atropine 1% eye drops include photophobia, blurred vision, decreased lacrimation and allergic reactions such as papillary conjunctivitis, contact dermatitis and lid edema. Systemic side effects rarely occur but include anticholinergic effects such as dryness of skin, mouth and throat from decreased secretion from mucus membranes, flushing, gastrointestinal symptoms, urinary retention and tachycardia. Systemic absorption may be reduced by gently compressing the lacrimal sac at the medial canthus for a minute during and following the instillation of the drops. This blocks the passage of the drops via the naso-lacrimal duct to the wide absorptive area of the nasal and pharyngeal mucosa.

The use of low-dose atropine has not yet been approved for the treatment of myopia and is not yet commercially available. In the ATOM 2 study, the reported side effects of atropine 0.01% and 0.1% were low. The pupil size under both photopic and mesopic conditions increased only 1 and 3 millimeters,

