respectively, in the 0.01% and 0.1% group. (32) Accommodation amplitude in the 0.01% group was reduced to only 11.3 diopters (from 16.2 diopters) compared with a reduction to 3.8 diopters (from 16.7 diopters) in the 0.1% group. The mean reduction in accommodation amplitude over 2 years treatment was 4.6 diopters and 10.1 diopters in the atropine 0.01% and 0.1% group, respectively. (32) In functional terms, the changes in accommodation meant that near visual acuity was not significantly impaired in the 0.01% group, whereas deficiencies were noted in the 0.1% group. (32) Mean distant best-corrected visual acuity (BCVA) was not affected by low-dose atropine, although 13% in both groups reported mild distance blur. (32) Regarding adverse reactions attributable to atropine, allergic reactions were most frequent in the ATOM 2 study with 3.2% experiencing allergic conjunctivitis and 0.8% experiencing an allergy-associated dermatitis, all of which were in the 0.1% group. From a total of 400 children, 6 children had other eye symptoms, 5 of which could be attributed to atropine treatment, including 1 case of ocular irritation and 1 case of blur in the atropine 0.01% group, and 2 cases of ocular irritation and 1 case of intolerable glare in the atropine 0.5% group. All reported side effects were reversible on stopping medication. No adverse events were deemed to be related to the use of atropine at any concentration. (32)

Patients who experience adverse effects during the study will provide data for the study to determine the rate of complications. Since the sample size calculation was made to account for dropout, additional inclusion of participants to replace excluded participants is not intended.

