## Registration of adverse events

At all trial visits, patients are checked for adverse events to the investigational medicinal product. All visits include measuring distant BCVA, IOP, pupil size and accommodation. The patients and parents will also be asked for subjective complaints and symptoms related to the investigational medicinal product. The number of trial visits is illustrated in Figure 2. Patient and parents will be instructed to contact the investigators immediately if vision gets worse, the eye or eye surroundings turns red and/or painful or they become sensitive to light, or experience halos around light sources. If the patient experiences an adverse event or reaction within the trial period, the patient will be monitored and/or treated for as long as it is relevant given the circumstances. Principle investigators will make the decision.

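### The stated masking of examiners and families is not assured for the loading arm in months 0–6, which mainly affects symptom and tolerability outcomes

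*Combined protocol and SAP*

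**What the plan says.** The Blinding section commits to "masking the investigators, additional study team performing the ocular measurements, parents and patients to randomization status throughout the entire study period". The means it describes are a list kept under lock and pre-labelled bottles of similar appearance.

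Under Study design, the loading arm receives 0.1% for 6 months and 0.01% for 18 months. All arms then have 12 months without treatment.

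Risks, side effects and inconveniences reports, from the cited dose-comparison trial in Asian children: "The pupil size under both photopic and mesopic conditions increased only 1 and 3 millimeters" for 0.01% and 0.1% in that order; accommodation falling from 16.2 D to 11.3 D on 0.01%; and a "reduction to 3.8 diopters (from 16.7 diopters) in the 0.1% group". It also gives mean two-year reductions of 4.6 D and 10.1 D, and says that near acuity was impaired at 0.1% but not significantly at 0.01%.

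Registration of adverse events adds: "All visits include measuring distant BCVA, IOP, pupil size and accommodation". Families are also asked about symptoms at each visit. Standard visits include months 3 and 6.

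For autorefraction under unstable fixation, "readings are eliminated if cylinder values deviate more than 1 diopter from values obtained during stable fixation and/or obvious incorrect readings". Change in spherical equivalent at 36 months is a listed primary endpoint, beside axial length elongation.

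**The concern.** Matching bottles and a hidden list conceal the code. They do not conceal a drug effect that the protocol expects to be large and has measured at every visit. No section separates the staff who measure pupil and accommodation from those who take refraction, withholds those results, fixes the order of tests, or assesses whether masking held. The section on spectacles adds a cue, because the investigator judges requests for photochromatic or bifocal lenses prompted by drug effects.

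At stake first is the hypothesis that 0.1% is safe with tolerable side effects. Adverse effects are a secondary endpoint, depend on what families report and staff record, and arise for 0.1% inside the window in which the arm can be recognised. Near acuity is not a listed endpoint but is measured at the same visits. If these results are reported as double-masked, readers will give them more weight than the design supports. A secondary stake is the clause allowing autorefraction readings to be dropped as plainly wrong, since spherical equivalent is a primary endpoint.

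**Working it through.** **1. The plan's figures.** The before-and-after values give falls of 16.2 − 11.3 = 4.9 D (0.01%) and 16.7 − 3.8 = 12.9 D (0.1%). The stated mean two-year reductions are 4.6 D and 10.1 D. The 0.1% pair differs (12.9 against 10.1), perhaps because the time points differ, so I carry both.

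- Accommodation, 0.1% against 0.01%: 11.3 − 3.8 = 7.5 D, or 10.1 − 4.6 = 5.5 D.
- Accommodation, 0.1% against no drug effect: 12.9 D or 10.1 D.
- Pupil: 3 − 1 = 2 mm against 0.01%; 3 mm against no drug effect.

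**2. Recognition.** The documents give no SDs, so I assume a between-child SD of 2–4 D for accommodation and 0.6–1.2 mm for pupil change. For two normal groups with equal SD, a cut at the midpoint sorts a share Φ(difference / (2 × SD)) correctly.

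| Comparison | Difference | Smaller SD | Larger SD |
|---|---|---|---|
| Accommodation, 0.1% v 0.01% | 7.5 D | Φ(1.875) = 97% | Φ(0.94) = 83% |
| Same, two-year reductions | 5.5 D | Φ(1.375) = 92% | Φ(0.69) = 75% |
| Accommodation, 0.1% v no drug | 12.9 D | Φ(3.23) = 99.9% | Φ(1.61) = 95% |
| Same, two-year reduction | 10.1 D | Φ(2.53) = 99% | Φ(1.26) = 90% |
| Pupil, 0.1% v 0.01% | 2 mm | Φ(1.67) = 95% | Φ(0.83) = 80% |
| Pupil, 0.1% v no drug | 3 mm | Φ(2.50) = 99% | Φ(1.25) = 89% |

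Guessing would give 50%. Accommodation alone separates 0.1% from 0.01% in 75–97% of children.

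**3. Timing.** The strong cue exists at months 3 and 6, and the arm then moves to 0.01%. Change in spherical equivalent at month 36 uses two sessions: baseline, before treatment, and month 36, which is 36 − 6 = 30 months after the last 0.1% visit and 12 months after treatment stops. Bias at month 36 needs someone to remember, or look up, the earlier results.

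**4. Room for judgement.** The cylinder limit of 1 D is numeric. The standard-visit list also fixes how surplus valid readings are cut to five. Only the final clause of the discard rule is judgement, and only under unstable fixation. The screening list has the same discard rule but not the reduction to five, although screening values stand as baseline when the two visits are less than a month apart.

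**5. Upper bound on spherical equivalent.** Suppose the most extreme readings on one side are always deleted, leaving five. The mean shifts by the sum of the expected largest normal order statistics, divided by five.

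- 1 of 6 deleted: 1.267 / 5 = 0.25 within-session SD.
- 2 of 7 deleted: (1.352 + 0.757) / 5 = 0.42 within-session SD.

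With an assumed within-session SD of 0.15–0.25 D, this runs from 0.25 × 0.15 = 0.04 D to 0.42 × 0.25 = 0.11 D. If the extreme reading on either side were deleted without regard to arm, the expected shift would be zero.

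**6. What 0.1 D would do.** The sample-size section uses an SD of 0.69 D and half of 1.2 D, that is 0.6 D: 2 × (0.69 × (1.960 + 0.842) / 0.6)² = 20.8, which rounds up to the stated 21 per arm. With 97 randomised (about 32 per arm), SE = 0.69 × √(2/32) = 0.1725 D. A differential bias of 0.1 D with no true effect raises the two-sided 5% error to 8.9%. If the 36-month SD is instead 0.69 × √3 = 1.195 D, the error is 6.3%.

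**The case against.** A reader might infer that the loading arm is effectively open and that hand-picked readings bias a primary endpoint. The documents do not support that, for four reasons.

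- The endpoint is read 30 months after the last 0.1% visit, after a year without treatment.
- Discretion is confined to one clause, under unstable fixation. The text does not say who removes readings, or that one person does every test.
- The 0.04–0.11 D shift requires deletion in the same direction in essentially every loading-arm child.
- The recognition figures rest on assumed SDs and on means from Asian children, whose transfer to Danish children the Introduction leaves open. They also assume an examiner who knows roughly where the two distributions lie.

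All four stand, and they limit the point on spherical equivalent to a small, conditional risk. Axial length, taken by instrument until five readings agree within 0.05 mm, is little exposed. The comparison of 0.01% with placebo does not involve the loading arm.

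It can also be said that the Blinding section describes procedures and does not claim that drug effects go unnoticed. That does not answer the point. The section states that examiners and families remain masked for the entire study, while the side-effect section gives reasons why many would not. Even the smaller accommodation difference with the wider SD leaves about three in four children correctly sorted.

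**Conclusion.** The point holds in limited form. For the loading arm, masking of examiners and families in months 0–6 is not assured by the measures described. For an assumed accommodation SD of 2–4 D, about 75–97% of children on 0.1% and 0.01% would be told apart by accommodation alone. Separation from no drug effect is stronger, at about 90% or more. Actual recognition is not known, because the documents neither give SDs nor plan to assess masking.

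The main consequence is for symptom, adverse-effect and near-acuity results in that window, and so for the tolerability hypothesis on 0.1%. For spherical equivalent at 36 months the effect is probably small: at most about 0.1 D under a one-directional worst case, against the planned 0.6 D, and only if earlier results are carried forward. It is worth correcting because the remedy is cheap. It does not undermine the axial length comparison.

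**What to change.** 1. **Examinations (screening and standard visits).** Replace the final clause of the discard rule with fixed numeric limits on both sphere and cylinder, relative to the session median. A limit on cylinder alone would leave wrong sphere readings in the spherical equivalent. Use the same rule, and the same reduction to five readings, at screening and every visit, applied by script. Keep all raw readings from now on. Apply the rule to past visits only where raw readings were kept, which the documents do not state.
2. **Remaining visits, including month 36.** Hide earlier pupil, accommodation, symptom and spectacle entries from staff taking refraction and axial length. Those responsible for participant safety keep full access.
3. **Blinding section and final report.** State that masking was not assured for the loading arm in months 0–6, and interpret symptom and tolerability outcomes from that window as potentially unmasked.

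Recruitment closed at the end of April 2021, so the 0.1% period is probably over and the third step is disclosure rather than prevention. Follow-up was scheduled to April 2024, so the second step can protect whatever visits remain. It does not hide a same-day finding from someone who performs both sets of tests. The cost is protocol wording, an eCRF view setting, a short script and a more modest masking claim. No clinical procedure is added.

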#### Participants

#### Criteria for inclusion

Preferably, children with a history of progression will be included in the study but since reliable refractive history can be difficult to obtain, the inclusion criteria are subdivided by age groups:

- Children aged  $\geq$ 6-<9 years: myopia  $\leq$ -1 (spherical power) in at least one eye
- Children aged  $\geq 9 \le 12$  years: myopia  $\le -2$  (spherical power) in at least one eye
- Cylinder less than 1.5 diopters

#### Criteria for exclusion

- Myopia related to retinal dystrophies
- Collagen syndroms (Ehlers-Danlos syndrome, Marfan syndrome and Stickler syndrome)

- Other ocular pathology (e.g., amblyopia, strabismus)
- Previous eye surgery
- Previous use of agents thought to affect myopia progression, e.g. atropine, pirenzepine or 7methylxanthine (metabolite of caffeine and theobromine) and orthokeratology contact lenses
- Known allergy to atropine or any of the contents of the trial medication (active and in-active ingredients) used in the study
- Non-compliance to eye examinations
- Serious systemic health troubles (e.g., cardiac or respiratory illness) and developmental disorders and delays

#### Procedures for recruiting participants

Patients will be recruited from private practitioners in ophthalmology referring children to the 3 research centers at (1) Department of Ophthalmology, Rigshospitalet, (2) Department of Ophthalmology, Aarhus University Hospital and (3) Department of Ophthalmology, Vejle Hospital. In addition, patients can be referred to the research centers from optometrists/opticians, orthoptics or other health care professionals handling myopic children. Self-referral by patients and parents who have heard of the study from others will also be accepted.

The study will be announced to private practitioners in ophthalmology, optometrists/opticians and orthoptics at relevant ophthalmological conferences, meetings and magazines during spring, summer and autumn 2018. Ophthalmologist, optometrists/opticians and orthoptics who have expressed interest in in the study will be invited to informational meetings where the study, criteria for inclusion and study logistics will be presented in detail by the investigators. The written participant information describing the study in lay terms will be available for the ophthalmologist, optometrists/opticians and orthoptics to be distributed in their waiting rooms. A written parental authority will be attached to the participant information. Patients and parents who express an interest to participate in the study will be referred to the nearest research facility. Thus, the patient and parents will have ample time to read the information and consider if they want to participate before they are seen at the research facilities.

The written participant information for the parents, the written parental authority and a copy of subjects' rights in a health science research project are attached as appendices.

After referral, the patient and parents will be contacted by phone by an investigator and invited to a screening visit. At the screening visit, the patient and parents will receive oral and written information about the study and the patient will undergo a screening ophthalmological examination by the investigators. The screening ophthalmological examination will only be performed after the patient and parents have consented to study participation and a signed consent statement has been obtained from the parents. The patient and parents will be invited to bring a friend or relative to the screening visit. Patients who fulfill the inclusion criteria and none of the exclusion criteria will be offered participation in the study.

#### Informed consent

The patient and parents will receive oral and written information about the study at the screening visit. The screening visit takes place in a secluded room at one of the research facilities without disturbances or interruptions. The patient and parents will be offered at least a 24 hours reflection period and scheduled for a visit at a later time point to sign the consent form. Patients and parents who are offered reflection period may, on request, consent to study participation at the screening visit. Written informed consent will be obtained from the parents and verbal consent will be obtained from the patient.

As a rule, only an investigator can obtain informed consent and sign the consent form. However, the sponsor-investigator request to waive from this requirement so that involved study staff (i.e. project nurses and optometrists) can obtain informed consent and sign the consent form as described in this section. The study staff in question is skilled within the pediatric ophthalmology from daily work life and trained in the study protocol and protocol specific procedures. If the nurse or optometrist wants further assessment or a parent wished to consult a medical doctor, an investigator is accessible. The assignment of obtaining consent is delegated to study staff (i.e. project nurses and optometrists) under the responsibility of the local principal investigator.

If both parents share the legal custody of the child, both parents must sign the consent statement. A written parental authority may be made from one parent to the other parent to give consent on behalf of both parents to study participation. The written parental authority will state what the purpose is (i.e., the child's participation in the study) and a duration of the parental authority of 1 month. The written parental authority will be included in the material distributed from the private practitioner in ophthalmology and requested completed at the screening visit if one parent is unable to participate in the screening visit. If only one parent holds the legal custody of the child, only this parent must sign the consent statement. In

that case, the investigator will ensure the necessary documentation for the legal custody, e.g. by asking the parent to provide an extract from the CPR registry or a copy of the child custody verdict.

During the screening visit, the patient and parents will receive a new copy of the written participant information for the parents and a copy of subjects' rights in a health science research project.

The study staff who informs the patient and parents will be aware of the pedagogical circumstances related to informing a child or young person of the relevant age group. However, the study staff does not have to hold a pedagogical education. The patient will be informed and involved in the discussions with the parents about the study, to the extent that the patient is capable of understanding the investigational situation. The information will therefore be adapted to the patient's intellectual level and mental capability. The patient's own desire to participate will be given importance when applicable and relevant. Protest also means resistance which is not formulated orally but which is expressed by the patient's attitude, body language or resistance to examination. This also applies to the entire trial period. A consent from the parents will never implies that study participation will be forced against the patient's own will. The patient will not be legal age during the course of the study period.

If the patient and parents consent to study participation the consent can be withdrawn at any time without any consequences to the child or family.

Patient and parents will not be offered any remuneration for participation in the study.

